ICH	International Conference on Harmonisation
ICD	informed consent form
ID	Identification
IND	investigational new drug application
INR	international normalized ratio
IRB	institutional review board
IRT	interactive response technology
IUD	intrauterine device
LFT	liver function test
LSLV	last subject last visit
MAOI	monoamino oxydase inhibitor
MDMA	methylenedioxy methylamphetamine (ecstasy)
MHP	medical health practitioner
CCI	
N/A	not applicable
NSAID	nonsteroidal anti-inflammatory drug
CCI	
PANSS	positive and negative syndrome scale
CCI	CCI
PCD	primary completion date
PDE10A	phosphodiesterase 10A
PET	positron emission tomography
PI	principle investigator
CCI	principie investigator
POC	proof of concept
CCI	CCI
PT	prothrombin time
CCI	CCI
RNA	ribonucleic acid
SAE	serious adverse event
SAP	statistical analysis plan
CCI	CCI
SIB	suicidal ideation and behavior
SRSD	single reference safety document
TCA	tricyclic antidepressants
CCI	CCI
TMS	total motor score
11710	tomi motor secre

UHDRS	unified Huntington's disease rating scale
ULN	upper limit of normal
US	United States
UTN	Universal Trial Number
WBC	white blood cell

PROTOCOL SUMMARY

INDICATION

PF-02545920 is a highly selective phosphodiesterase 10A (PDE10A) inhibitor that is being developed for the symptomatic treatment of Huntington's disease (HD).

BACKGROUND AND RATIONALE

The Disease:

HD is an autosomal dominant neurodegenerative disease that targets the corticostriatal system and results in (1) progressive movement disorder, initially manifesting as chorea; (2) progressive cognitive disturbance culminating in dementia; and (3) various behavioral disturbances that often precede diagnosis and can vary depending on the state of disease. The mean age of onset is 35-44 years and the median survival time is 15-18 years after onset.

HD is caused by an expansion of a translated trinucleotide cytosine adenine guanine codon or CAG, coding for a glutamine repeat in the 5'- region of the *Htt* gene on the short arm of chromosome 4, resulting in widespread corticostriatal pathology.

The diagnosis of HD relies on characteristic clinical findings and the detection of an expansion of CAG equal to or greater than 36 repeats in the *Htt* gene, which is often associated with a positive family history.

The neuropathological hallmark of HD is the accumulation of aggregates of mutated huntingtin protein and progressive loss of medium spiny neurons (MSNs), beginning in the dorsal medial head of the caudate with subsequent progression to the ventrolateral striatum with significant, if less pronounced, neuronal loss in other subcortical and cortical structures.

The Compound:

PF-02545920 is a highly selective PDE10A inhibitor. PDE10A is an enzyme which is highly enriched in the MSNs of the striatum and has an important role in the regulation of cAMP and cGMP levels. PF-02545920 is a selective inhibitor of PDE10A in *in vitro* systems. Reduced PDE10A mRNA and protein levels have been found in homogenates from the striatum of HD subjects. Results from a recent pilot positron emission tomography (PET) imaging study with the PDE10A ligand [¹8F]MNI-659 showed decreased PDE10A binding sites in HD stage I/II patients as expected, consistent with the degeneration of MSNs in HD. A cross-sectional study on quantification of PDE10A levels in pre-manifest, early and mid-stage disease HD subjects and healthy volunteers is currently ongoing at the Karolinska Institute. Preliminary results from this study confirmed previous reports suggesting that PDE10A enzyme expression in HD brain is compatible with further clinical development of PF-02545920 for the symptomatic treatment of HD. Preclinical HD models have demonstrated that PDE10A enzyme levels ≥20% of normal can elicit robust biochemical signatures by increasing cyclic nucleotide signaling in response to PDE10A inhibition.

In vivo PF-02545920 administration results in increased striatal levels of cGMP and cAMP and in the putative activation of a number of downstream signaling molecules regulated by cyclic nucleotide cascades in MSNs, leading to overall increased striatal activation and decreased locomotor hyperactivity.

The Mechanism:

Preclinical studies conducted in collaboration with the Cure Huntington's Disease Initiative (CHDI) Foundation, Inc. demonstrated that PDE10A inhibition is effective in reversing multiple parameters of aberrant excitability of MSNs, and in improving elements of corticostriatal connectivity in brain slices derived from symptomatic R6/2 and Q175 knock-in mice. Chronic (4 months) dosing of Q175 HD transgenic mice with PF-02545920 significantly improves dysfunction of the corticostriatal circuits, which develops with disease progression.

Moreover, recent studies in two additional transgenic models of HD using a bacterial artificial chromosome, BACHD mice and BACHD rats, showed that both acute and chronic (2 weeks) administration of PF-02545920 results in functional improvement of indirect pathway activity. Most importantly, *in vivo* functional improvement measured as a reversal of the impaired subthalamic nucleus firing rate was demonstrated in the full length mHtt transgenic BACHD rat following acute treatment with PF-02545920.

In summary, these preclinical observations suggest that treatment with PF-02545920 preferentially improves activity of the indirect pathway of the basal ganglia, which is primarily impaired in the earlier stages of HD, and thus it may lead to functional normalization of affected corticostriatal brain circuitry and alleviate motor symptoms, and potentially behavioral and cognitive symptoms in individuals with HD.

Complete information for this compound may be found in the single reference safety document (SRSD), which for this study is the Investigator Brochure.

Safety:

To date, evaluation of PF-02545920 has been completed in 7 clinical studies included in the 2014 Investigator Brochure.

Interpretation of the study results and the possible risks associated with the administration of PF-02545920 are summarized in Section 7 of the Investigator's Brochure (IB 2014 version).

Dose Rationale:

Based on the previous pre-clinical efficacy data and clinical safety data, a dose of 20 mg is estimated to produce the most robust PDE10A inhibition while still being well tolerated. Therefore, the present study with 20 mg BID PF-02545920 will continue to evaluate safety and tolerability in subjects with HD. A double blind titration scheme will be used to mitigate the potential risk of dystonia for subjects who did not receive 20 mg in the preceding study (A8241021). The incidence rate of dystonia for the titrated 15 mg BID dose group in study A8241012 was substantially lower than the rate observed in a similar study (A8241006) population with a non-titrated 15 mg BID dosing regimen.

STUDY OBJECTIVES

Primary Objective:

• To assess long-term safety and tolerability of 20 mg BID of PF-02545920 in subjects with HD.

Secondary Objectives:

- To assess motor function after 6 and 12 month oral dosing with 20 mg BID of PF-02545920 in subjects with HD.
- To assess the efficacy of 6 and 12 month oral dosing with 20 mg BID of PF-02545920 on chorea severity in subjects with HD.
- To assess whether 6 and 12 month oral dosing with 20 mg BID of PF-02545920 can improve the overall clinical impression in subjects with HD.

STUDY ENDPOINTS

Primary Endpoint:

[figure not shown]
• Adverse events, weight, vital signs (pulse, blood pressure and body temperature), physical examination, neurological examination, electrocardiogram (ECG) and

clinical laboratory findings (hematology, biochemistry and urinalysis). The endpoints are:

- The number and proportion of subjects with adverse events.
- Assessment of clinical laboratory parameters.
- Assessment of vital signs.
- Assessment of ECG parameters.
- White blood count (WBC) and absolute neutrophil count (ANC) at each visit.
- Abnormal laboratory findings from baseline.
- Frequency and severity of adverse events related to extrapyramidal symptoms (EPS) including dystonia and akathisia, as assessed by the investigator.
- C-SSRS (suicide severity assessment).

Secondary Endpoints:

- Change from baseline in the Total Motor Score (TMS) assessment of the Unified Huntington Disease Rating Scale (UHDRS) after 6 and 12 months of treatment.
- Change from baseline in the Total Maximum Chorea (TMC) score of the UHDRS after 6 and 12 months of treatment.
- Clinical Global Impression-Improvement score after 6 and 12 months of treatment.

STUDY DESIGN

[figure not shown]
This study is a 12 month open label extension study, following study A8421021, with a single dose of 20 mg PF-02545920 BID for the treatment of motor impairment of subjects with HD. Subjects, who received 20 mg BID of PF-02545920 in the preceding study A8241021, will receive 20 mg BID of PF-02545920 in this study without any titration. A double blind titration scheme will be used to mitigate the potential risk of dystonia for those subjects who did not receive 20 mg in the first study (A8241021).

20 mg BID PF-02545920 (up to 260 subjects)

- Titration schedule for subjects previously not assigned 20mg PF-02545920:
 - 5mg BID x 7 days
 - 10mg BID x 7 days
 - 15mg BID x 7 days
 - 20mg BID to Month 12

5mg step de-escalation option available for

intolerable AE

For Screening procedures and assessments investigator will use data from Week 13 and Week 19 Visits from the A8241021 study

For Baseline procedures and assessments investigator will use data from Week 26 Visit from the A8241021 study along with additional Baseline assessments

SCHEDULE OF ACTIVITIES

The schedule of activities table provides an overview of the protocol visits and procedures. Refer to the STUDY PROCEDURES and ASSESSMENTS sections of the protocol for detailed information on each procedure and assessment required for compliance with the protocol.

The investigator may schedule visits (unplanned visits) in addition to those listed on the schedule of activities, in order to conduct evaluations or assessments required to protect the well-being of the subject.

Visit Window		Day (±	3 days) ¹	Day (±7 days) ¹					
Visit Identifier	Screening ²	Baseline ³	Week 2	Week 4	Month 3	Month 6	Month 9	Month 12 /ET ⁴	Follow up ⁵
Visit Number	V1	V2	V3	V4	V5	V6	V7	V8	V9
Study Day		Day 1	Day 14	Day 28	Day 91	Day 182	Day 273	Day 365	Day 372 to 379
Informed Consent	X								
CCI	CCI								
File Record of Signed and Dated Pre-screening Checklist A ⁶	X								
Complete Screening Checklist B for review of study A8241021 data ⁶	X								
Review Inclusion/Exclusion Criteria	X	X							
CAG profile documentation		$(X)^7$							
Demography		$(X)^7$							
Review Medical History and Prior/Concomitant Medications		X							
Review Adverse Events (AE) & Changes since last visit (medical history, procedures, con. meds)			X	X	X	X	X	X	X
Height		$(X)^7$							
Weight		$(X)^8$				X		X	
Brief Physical Examination		$(X)^8$				X		X	X
Brief Neurological Examination		(X) ⁸				X		X	X
Electrocardiogram (ECG) ⁹		(X) ⁸			X	X	X	X	
Supine and Standing Blood Pressure and Pulse (orthostatic vitals); Body Temperature ¹⁰		(X) ⁸				X		X	

Visit Window		Day (±3	3 days) ¹	Day (±7 days) ¹					
Visit Identifier	Screening ²	Baseline ³	Week 2	Week 4	Month 3	Month 6	Month 9	Month 12 /ET ⁴	Follow up ⁵
Visit Number	V1	V2	V3	V4	V5	V6	V7	V8	V9
Study Day		Day 1	Day 14	Day 28	Day 91	Day 182	Day 273	Day 365	Day 372 to 379
Sitting Blood Pressure and Pulse; Body Temperature (standard vital signs) ¹⁰			X	X	X		X		X
Contraception Check		(X) ⁸	X	X	X	X	X	X	
Laboratory tests: ¹¹									
Hematology ¹²		(X) ⁸	X ¹²	X ¹²	X	X	X	X	X ¹²
Blood Chemistry		(X) ⁸				X		X	
Serum Pregnancy Test		(X) ⁸			X	X	X	X	
Urine Pregnancy Test		X							X
Serum FSH ¹³		X							
Urinalysis		(X) ⁸				X		X	
Urine drug screen ¹⁴		X							
CCI									
Assessments:									
C-SSRS Since Last Visit		(X) ⁸	X	X	X	X	X	X	X
CCI		8							
		G							
			_	_	_		_		
CCI									

Visit Window			Day (±.	3 days) ¹		Day (±	7 days) ¹		
Visit Identifier	Screening ²	Baseline ³	Week 2	Week 4	Month 3	Month 6	Month 9	Month 12 /ET ⁴	Follow up ⁵
Visit Number	V1	V2	V3	V4	V5	V6	V7	V8	V9
Study Day		Day 1	Day 14	Day 28	Day 91	Day 182	Day 273	Day 365	Day 372 to 379
CCI		CCI				CCI		CCI	
CCI									
ANC and WBC Review ¹⁷	X	(X) ⁸	X	X	X	X	X	X	X
Site Eligibility Review ⁶ Sponsor Eligibility Verification ¹⁸ and Documentation of Confirmation	X X	X							
Randomization ¹⁹		X							
CCI 20									
CCI CCI						GGI		ec.	
		GGI							
Diameter live		V							
Dispense dosing diary Dispense study drug for outpatient dosing		X X	X	X	X	X	X		
Subject instruction on outpatient dosing		Λ	Λ	Λ	Λ	Λ	Λ		
from blister packs/bottles, dosing diary use and reporting AEs and SAEs.		X							
Assess compliance based on observation of blister packs, pill counts, review dosing diary			X	X	X	X	X	X	
Collect dosing diary				X					

Footnotes:

- 1. All visits windows are relative to the V2 Baseline Day 1 visit date.
- 2. Screening visit will take place during the Week 19 Visit for study A8241021.
- 3. Baseline Day 1 activities will take place during Week 26 Visit for Study A8241021.
- 4. In case of Early Termination between Baseline and Day 14 (exclusive), only safety assessments will be performed (See STUDY PROCEDURES). If Early Termination occurs after Day 14 (inclusive), as many Month 12/ET assessments as possible should be completed.
- 5. Follow-up visit is to take place 7 to 14 days after the last dose on Month 12 (V8).
- 6. Site eligibility review: the site will review all laboratory test results, pregnancy test, ANC and WBC, drug test results, against I/E criteria. Checklists A and B will be provided to the site by the sponsor.
- 7. Data collected at Screening for Study A841021 will be used.
- 8. Assessment results collected at Week 26 for Study A8241021 will be used for Baseline Day 1 (V2).
- 9. Single 12-lead ECG will be recorded at Baseline Day 1 (V2) and collected at Month 3 (V5), Month 6 (V6), Month 9 (V7) and Month 12/ET (V8).
- 10. Vital signs to include blood pressure, pulse and oral or tympanic body temperature.
- 11. Samples for laboratory can be obtained without regard to fasting status.
- 12. Hematology samples will be collected only for ANC and WBC safety monitoring at Week 2 (V3), Week 4 (V4) and Follow-up (V9).
- 13. Serum FSH may be performed to confirm postmenopausal status for females who have been amenorrheic for at least 12 consecutive months.
- 14. Urine Drug screen may be performed at Baseline Day 1 (V2) and any time at the discretion of the investigator.

15.**CCI**

- 16. CGI-S will be administered once at Baseline Day 1 (V2); CGI-I will be administered at Month 6 (V6) and Month 12 (V8) or Early Termination.
- 17. The site will perform and document ANC and WBC review at all visits for neutropenia safety monitoring. A source document worksheet will be provided by the sponsor to ensure this is documented and monitored carefully throughout the course of the study.
- 18. Sponsor Eligibility Verification process: The Sponsor will verify key elements of the study inclusion/exclusion criteria prior to randomization of each subject. All information related to subject eligibility, including, but not limited to, HD diagnosis and screening safety laboratory data, electrocardiograms, and Vital Sign results from study A8241021, should be entered in the subject eCRF and available for sponsor review. Investigators will be trained on the Screening Verification process, as part of the protocol training prior to study start.
- 19. Randomization code can be obtained by the clinical sites as soon as the sponsor has verified that the subject is eligible (2 business days reserved at the end of the Screening period).

20. CC

[figure not shown]

TABLE OF CONTENTS

LIST OF TABLES	22
LIST OF FIGURES	22
APPENDICES	22
1. INTRODUCTION	23
1.1. Mechanism of Action/Indication	23
1.2. Background and Rationale	23
1.2.1. Drug Development and Study Rationale:	23
1.2.2. Safety and Clinical Data	25
1.2.3. Pharmacokinetics	29
1.2.4. Dose Selection Rationale	30
2. STUDY OBJECTIVES AND ENDPOINTS	30
2.1. Objectives	30
2.2. Endpoints	31
3. STUDY DESIGN	33
3.1. Stopping Criteria	34
3.1.1. Subject Stopping Criteria	35
3.1.2. Study Stopping Criteria	35
4. SUBJECT SELECTION	35
4.1. Inclusion Criteria	35
4.2. Exclusion Criteria	36
4.3. Randomization Criteria	40
4.4. Lifestyle Guidelines	40
4.4.1. Activity	40

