5.1. Allocation to Treatment

The investigator's knowledge of the treatment should not influence the decision to enroll a particular subject or affect the order in which subjects are enrolled.

Investigators will use an Interactive Response Technology (IRT) to assign a unique subject identification number to each subject who has signed the informed consent document (ICD). This identifying number will be retained throughout the duration of the study participation. Subject eligibility for participation in the study will be determined following the Screening assessments (V1). Once the subject is determined to be eligible for treatment, the investigator will obtain a randomization number and study medication assignment utilizing the IRT.

Subjects, who received PF-02545920 20 mg BID in the preceding A8241021 study, will continue to receive PF-02545920 20 mg BID in this study. Subjects, who previously received either PF-02545920 5 mg BID or placebo in the A8241021 study, will be titrated to PF-02545920 20 mg. The titration will start at 5 mg BID and the dose will be increased by 5 mg BID every 7 days, up to a 20 mg BID to be reached at Day 22, and maintained until Month 12 (V8). Subjects will take 4 tablets twice a day provided in blister packs from Baseline Day 1 (V2) to Week 4 (V4) and in bottles from Week 4 (V4) to Month 12 (V8). For subjects, who have been de-escalated from 20 mg BID to lower dose in the preceding study A8241021, the investigator should contact the sponsor study clinician and medical monitor to discuss titration scheme.

Table 3. Allocation to Study Treatments

Treatment Group	Study Treatment	Drug Administration	Duration
20 mg PF-02545920, Subjects receiving 20 mg PF-02545920 in the preceding A8241021 study	Days 1-365 Four 5 mg tablets of PF-02545920	Orally, BID	12 months (Days 1-365)
20 mg PF-02545920, All other subjects	Days 1-7 One 5 mg tablet of PF-02545920 Three placebo tablets for PF-02545920 Days 8-14 Two 5 mg tablets of PF-02545920 Two placebo tablets for PF-02545920 Days 15-21 Three 5 mg tablets of PF-02545920 One placebo tablet for PF-02545920	Orally, BID	12 months (Days 1-365)
	Days 22-365 Four 5 mg tablets of PF-02545920		

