6.2.4. Visit 5 – Month 3/Day 91 (±7 days)

The following activities will be completed during Month 3 visit (V5):

- Review adverse events since last visit.
- Review changes in the subject's medical history, concomitant medications, and medical procedures since last visit.
- Obtain vital signs (sitting blood pressure and pulse; oral or tympanic body temperature).
- Obtain standard 12-lead ECG (may be repeated if clinically indicated).
- Contraception check.
- Collect non-fasted blood sample for Hematology.
- Serum pregnancy test for females of child bearing potential.
- CCI
- Complete C-SSRS (since last visit) for suicidality risk assessment.
- Administer the UHDRS Total Motor Score (TMS).
- Review ANC and WBC for safety monitoring.
- Assess compliance based on counting of unused tablets in bottles.
- Dispense study drug to subject for outpatient dosing, with instructions to return to next clinic visit with all (used and in-use) bottles.
- Remind the subject about the date of the next scheduled Month 6 visit (V6).

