6.2.5. Visit 6 – Month 6/ Day 182 (±7 days)

The following activities will be completed during Month 6 visit (V6):

- Review adverse events since last visit.
- Review changes in the subject's medical history, concomitant medications, and medical procedures since last visit.

- Obtain weight (kilograms).
- Perform brief physical examination.
- Perform brief neurological examination.
- Obtain standard 12-lead ECG (may be repeated if clinically indicated).
- Obtain orthostatic vital signs (supine and standing blood pressure and pulse) and oral or tympanic body temperature.
- Contraception check.
- Collect non-fasted blood sample for routine laboratory tests, including the following tests:
 - Hematology;
 - Blood chemistry;
 - Obtain serum sample for pregnancy test for females of child bearing potential (sent to central lab).
- Collect urine sample for urinalysis.
- CCI
- Complete C-SSRS (since last visit) for suicidality risk assessment.
- CCI
- Administer the UHDRS Total Motor Score (TMS), CCI (Section 7.9.1).
- CCI
- CCI (CCI)
- Complete CGI-I scale.
- CCI (CCI);

- CCI ;
- CCI
- CCI
- CCI CCI
- Review ANC and WBC for safety monitoring.
- Assess compliance based on counting unused tablets in bottles.
- Dispense study drug to subject for outpatient dosing, with instructions to return to next clinic visit with all (used and in-use) bottles.
- Remind the subject about the date of the next scheduled Month 9 visit (V7).

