6.2.9. Unscheduled Visit

Unscheduled visits may be performed at any time during the study, whenever necessary to assess or to follow-up on adverse events (AE) or serious adverse events (SAE) at the subject's request, or as deemed necessary by the investigator. The following clinical evaluations should take place, as medically warranted in the judgment of the investigator:

- Physical examination.
- Neurological examination.
- 12-lead ECG, when clinically indicated to follow-up on any prior clinically significant ECG abnormalities.
- Vital signs (supine and standing).
- Laboratory safety assessments, when clinically indicated to follow-up on any prior clinically significant laboratory abnormality.
- Review study drug compliance and accountability (if applicable).
- Review and record adverse events (AE) and serious adverse events (SAE).
- Review of prior and concomitant medications.
- Subject education on how to maintain compliance.

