7.6. Blood Volume

Total blood sampling volume for the individual subjects is approximately 112 mL. The actual times of blood sampling may change but the total blood volume collected will not increase. Additional blood samples may be taken for safety assessments at times specified by Pfizer, provided the total volume taken during the study does not exceed 550 mL during any period of 30 consecutive days and the IRB/EC is notified of the blood collection.

Sample Type	Blood Sample	Number of Sampling Times						Total Volume (mL)			
	Volume (mL)	Screening	Bsl	V3	V4	V5	V6	V7	V8	FU	
Routine lab tests 1	7		(1)			1	1	1	1		35
Safety lab monitoring (ANC/WBC)	7			1	1					1	21
Serum Pregnancy test ²	3		(1)			1	1	1	1		15
Serum FSH ²	5		1								5
TOTAL.	CC		(°C)		CC	CC	CC	CC	CC		112

Table 5. Blood Volume

- 1. Includes hematology and blood chemistry.
- 2. Female only.
- 3. Numbers in parentheses will be collected only if missed or abnormal in study A8241021.

This total volume does not include any discarded blood from pre-draws used to remove fluid from flushed catheters.

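### Blood chemistry is first scheduled 160 days after newly titrated subjects reach 20 mg BID; ordering it at the existing Month 3 draw cuts this to 69 days at little cost

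*Protocol*

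**What the plan says.** The chemistry row of the protocol's Schedule of Activities reads "Blood Chemistry (X) ⁸ X X". The marks fall under Baseline, Month 6 (V6) and Month 12/ET (V8), and the baseline value is the parent study's (A8241021) Week 26 result. The visit instructions agree with the row. At Month 3, Section 6.2.4 says "Collect non-fasted blood sample for Hematology", and Section 6.2.6 says the same for Month 9. Chemistry first appears at Month 6, where Section 6.2.5 says "Collect non-fasted blood sample for routine laboratory tests, including the following tests" and lists hematology and blood chemistry; Section 6.2.7 repeats this for Month 12.

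Section 5.1 has subjects from placebo or 5 mg BID titrated in weekly 5 mg steps, "up to a 20 mg BID to be reached at Day 22". Section 5.2 makes this titration period double blind.

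Table 5 (Section 7.6) does not match these orders. It counts V5 (Month 3) and V7 (Month 9) as routine laboratory draws, with the footnote "Includes hematology and blood chemistry". A separate row covers the ANC/WBC-only draws at V3, V4 and follow-up.

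Chemistry outside the schedule is possible. The introduction to the Schedule says "The investigator may schedule visits (unplanned visits) in addition to those listed on the schedule of activities", Section 6.2.9 says "Unscheduled visits may be performed at any time during the study", and Section 7.6 says "Additional blood samples may be taken for safety assessments at times specified by Pfizer".

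**The concern.** Biochemistry is a component of the primary safety endpoint. The rule for potential drug-induced liver injury (Section 8.6.2) works only if transaminases and bilirubin are measured together. For a subject new to 20 mg BID, the baseline panel predates that dose and the next scheduled panel is at Month 6. In between, blood is drawn at Week 2, Week 4 and Month 3, but no chemistry is ordered on it.

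The gap is narrow. A subject with symptoms can be seen and tested at any time. What has no routine trigger before Month 6 is a chemistry change without symptoms. The laboratory item in the Section 6.2.9 list is tied to following up an earlier clinically significant abnormality, so it does not prompt a first look. Potential Hy's law cases are reported as SAEs and the E-DMC can meet ad hoc, but both depend on a sample having been taken.

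**Working it through.** The check is arithmetic on scheduled study days. No detection probability is claimed.

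**Inputs**
- Titration: three 7-day steps below 20 mg BID (Section 5.1, Table 3).
- Visit days: Month 3 = Day 91, Month 6 = Day 182, Month 9 = Day 273, Month 12 = Day 365, each ±7 days (Schedule; Sections 6.2.4 to 6.2.7).
- Panel content: ALT, AST, total bilirubin and creatine kinase are in the chemistry column of Table 6.
- Blood volume: 7 mL per routine draw at Baseline, V5, V6, V7 and V8 (Table 5).

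**The plan's own figures**
- First day at 20 mg BID: 1 + 3 × 7 = Day 22, as Section 5.1 states.
- Table 5 routine row: 7 mL × 5 draws = 35 mL, as stated. The V5 and V7 draws are therefore already counted.
- Table 5 ANC/WBC row: 7 mL × 3 = 21 mL, as stated.

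**Intervals without scheduled chemistry (days)**

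| Interval | Current plan | Month 3 added | Months 3 and 9 added |
|---|---|---|---|
| First 20 mg BID dose to first chemistry (newly titrated) | 182 − 22 = 160 (153 to 167) | 91 − 22 = 69 (62 to 76) | 69 (62 to 76) |
| First dose to first chemistry | 182 − 1 = 181 (174 to 188) | 91 − 1 = 90 (83 to 97) | 90 (83 to 97) |
| Month 3 to Month 6 | not applicable | 182 − 91 = 91 (77 to 105) | 91 (77 to 105) |
| Month 6 to Month 12 | 365 − 182 = 183 (169 to 197) | 183 (169 to 197) | 273 − 182 = 91, then 365 − 273 = 92 |

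Ranges use the ±7-day window at one visit, or at both visits where the interval runs between two.

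**Extra panels**, at the protocol's maximum of 260 subjects: 260 × 1 = 260 for Month 3 alone; 260 × 2 = 520 for both visits.

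**Do the orders and Table 5 agree?** No. The Schedule and Sections 6.2.4 and 6.2.6 give hematology only at Months 3 and 9, while Table 5 puts those visits in the hematology-plus-chemistry row. Table 5 allots the same 7 mL at V6 and V8, where both panels are ordered. On its own accounting, then, chemistry at V5 or V7 adds no volume: the row stays at 35 mL and the stated total at 112 mL.

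**The case against.** The strongest reply is that half-yearly chemistry is a defensible choice for this compound. Monitoring is matched to the named risks, neutropenia and EPS. A8241012 found no significant laboratory differences between groups, A8241018 found no clinically important laboratory trends, and the ongoing studies had produced no new unexpected adverse events by August 2014. Entry rules limit AST/ALT to 2 × ULN and total bilirubin to 1.5 × ULN (with a Gilbert's provision). Subjects from the 5 mg arm already have lower-dose exposure. The parent study's 20 mg BID results and the Investigator's Brochure, which we cannot see, may reassure further.

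Much of this stands, and it limits the claim to a gain in monitoring. It does not remove the point:
- The two laboratory statements come from studies dosed up to 15 mg BID. Outside the parent study, the multiple-dose experience at 20 mg BID described in the protocol lasted 13 days (A8241002) and 28 days (A8241016).
- The parent study's 20 mg arm may lower concern about the drug in general, but it does not monitor a subject who took placebo or 5 mg in it.
- ECGs are scheduled at Months 3, 6, 9 and 12 although A8241012 and A8241018 reported no ECG concern. The absence of a signal therefore does not by itself explain leaving chemistry off the Month 3 draw.
- The entry limits admit mildly raised liver values, and Section 8.6.2 gives such subjects baseline-adjusted thresholds that need later measurements.

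Other objections also stand in part. Table 5 is a volume table and does not order tests. It gives 7 mL to ANC/WBC-only draws too, so the volume does not prove that chemistry was intended at Month 3. Month 3 leaves the longest interval, 183 days, unchanged and still leaves 69 days at full dose. CK adds little, since no visible rule acts on a CK threshold. Extra panels will probably produce some incidental abnormalities that need follow-up.

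**Conclusion.** The point holds as a low-cost improvement. Newly titrated subjects have 160 days (153 to 167) at 20 mg BID before a scheduled chemistry; using the existing Month 3 draw makes this 69 days (62 to 76). The figures assume titration on schedule and no unscheduled or early-termination chemistry. They do not apply to subjects continuing on 20 mg BID, whose Week 26 panel was taken on treatment. No harm is shown and no detection rate is estimated. Separately, Table 5 and the visit orders disagree at Months 3 and 9, and one of them needs correcting in any case. SAP Section 8.1 records that the study ended unexpectedly, so the point bears on the design as written and on any protocol that reuses this schedule.

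**What to change.** **Main change.** Mark blood chemistry at Month 3 (V5) in the Schedule row and add it to Section 6.2.4. Order it for all subjects, because testing only the titrated ones would reveal the blinded titration assignment.

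**Secondary change.** Do the same at Month 9 (V7) in the Schedule and Section 6.2.6. This does nothing for the newly titrated gap, but it splits the Month 6 to Month 12 interval and aligns the orders with Table 5.

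**If either visit is declined.** Correct footnote 1 of Table 5 so that it no longer describes that draw as including chemistry.

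**Cost.** A protocol amendment with IRB/EC approval (two edits for Month 3, two more for Month 9), which can be bundled with another amendment. Laboratory fees and investigator review for at most 260 or 520 panels, plus follow-up of any incidental abnormalities; the documents give no fee. No new visit or venepuncture for the scheduled panel, and no extra volume by Table 5. No SAP change: SAP Section 8.3.7 summarizes laboratory data by sponsor standards without naming chemistry visits, and Appendix 3 already has Month 3 and Month 9 windows.
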